Objectives	 Secondary Objectives Progression-Free Survival Overall Survival Measurement of changes in circulating tumor DNA (ctDNA) KRAS allelic frequency Measurement of changes in biomarkers related to autophagy 				
Number of Subjects	 Stage 1: 10 patients Stage 2: 19 patients Total: Up to 29 patients Must be ≥ 18 years of age. Metastatic or incurable NSCLC Presence of a non-synonymous mutation in KRAS Must have received at least one prior systemic therapy for metastatic NSCLC, or be intolerant/otherwise ineligible for such therapy 				
Diagnosis and Main Inclusion/Exclusion Criteria	 Must have ECOG performance status of 0 or 1 Must have adequate renal, liver, cardiac and hematological function Must be able to provide written informed consent. Must have at least one measurable lesion according to Response Evaluation Criteria for Solid Tumors (RECIST 1.1) Patients with asymptomatic or treated, stable brain metastases are allowed to enroll. Patients with carcinomatous meningitis are excluded. 				

Study Product, Dose, Route, Regimen	Hydroxychloroquine 400 mg by mouth every 12 hours (obtained commercially), binimetinib 45 mg 2 times daily				
Duration of administration	Until progression, unacceptable toxicity, or withdrawal of consent.				
Study design	Phase 2: Optimal Simon 2-stage design with the first stage recruiting 10 patients, and 19 additional patients if there are ≥ 2 responses seen.				
Duration of trial	 Approximately 2 years Follow-up: All subjects will be evaluated per study calendar for 6 months after discontinuation of study treatment All subjects will be followed for a minimum of one year from the start of treatment, unless disease progression is reported prior to one year. 				

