4.5 Duration of Protocol Treatment and Follow-up

Treatment will continue until disease progression and may continue at the discretion of the treating physician in consultation with the Principal Investigator, if there is an isolated progression. Treatment may also be discontinued for adverse events that delay treatment greater than 28 days and as outlined in Toxicities and Dose Modifications. Please refer to Off Treatment/Off Study for additional reasons for study withdrawal. Subjects will be evaluated for at least 6 months after discontinuation of study treatment and will be followed for a minimum of one year from the start of treatment, unless disease progression is reported prior to one year. One year survival information will be extracted from the medical record or by phone call for subjects who have discontinued protocol treatment and completed the 6 month follow-up evaluations prior to one year from the start of treatment.

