4. Required q12 weeks (i.e. approximately every 3 cycles). ECHO to be performed between D21-D28 for applicable cycle

- Subjects who discontinue study treatment in the absence of disease progression will have post-treatment follow-up as per standard of care for disease status until one of the following events: (1) disease progression; (2) initiation of non-study cancer treatment; (3) withdrawal of study consent; (4) loss to follow-up; or (5) death. The subject will then enter into survival follow-up. Subjects who discontinue study treatment due to disease progression or initiation of a new anti-cancer therapy will enter survival follow-up directly. Survival follow-up will continue up to 1 year from initiation of study treatment (Cycle 1/Day 1).
- 6. RECIST 1.1 will be used in this study for assessment of tumor response. While either CT or MRI may be utilized, as per RECIST 1.1, CT is the preferred imaging technique in this study. Tumor imaging timing should follow calendar days and should not be adjusted for delays in cycle starts or extension of cycle duration. All visceral areas originally involved by tumor should be re-imaged at each scan interval. The preferred type of imaging is high resolution CT scans of the chest abdomen and pelvis with contrast. In cases of elevated creatinine or anaphylactic reaction to contrast dye, CT scans without contrast or MRI with gadolinium may be substituted for the abdomen and non-contrast CT for the chest.
- 7. The 30 day Safety Follow-up Visit must occur prior to the first dose of any new anti-cancer therapy.
- 8. Baseline tumor imaging to be performed within 30 days prior to Cycle 1/Day 1

UPCC 21520

- 9. Tumor imaging to be performed after every 2 cycles(approximately every 2 months after C1D1 on D21-D28 of applicable cycle).
- 10. CBC with differential including hemoglobin, white blood count, absolute neutrophil count, and platelet count. Serum chemistries including sodium (Na), potassium (K), chloride (Cl), bicarbonate (HCO3), blood urea nitrogen (BUN), creatinine (Cr), albumin, total bilirubin, AST, ALT, and alkaline phosphatase. After Cycle 1, pre-dose laboratory procedures can be conducted up to 72 hours prior to dosing. Results must be reviewed by the investigator or qualified designee and found to be acceptable prior to each dose of trial treatment.
- 11. Screening laboratory tests are to be performed within 10 days prior to Cycle 1/Day 1.

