- 12. Treatment will continue indefinitely in the absence of (1), documented disease progression, (2) unacceptable adverse event(s), (3) intercurrent illness that prevents further administration of treatment, (4) investigator's decision to withdraw the subject, (5) subject withdrawal of consent, (6) pregnancy of the subject, (7) noncompliance with trial treatment or procedure requirements, (8) institution of alternative systemic treatment, or (9) other administrative reasons.
- 13. Tumor imaging in post-treatment follow-up will be performed per routine care and at the discretion of the treating investigator.
- 14. See table 3 for required time-points. Suspicion for eye toxicity will prompt an unscheduled research eye exam. To assure the ocular safety of the subjects, at each ocular exam visit the Ophthalmology sub-Investigator will perform a comprehensive eye examination of both eyes. The specified assessments within the ophthalmic examination are reflective of consensus guidelines [American Academy of Ophthalmology Preferred Practice Patterns Committee, 2005] and will be performed according to the Investigator's usual practice in addition to the assessment of visual acuity in the study and will include:

-Ocular alignment and motility, pupillary function, and visual fields by confrontation

-External examination of the eyelids and eyelashes

-Slit-lamp biomicroscopic examination of the anterior segment structures: eyelid margins, conjunctiva, sclera, cornea, anterior chamber, iris, lens, and anterior vitreous

-Intraocular pressure (IOP) measurement

-Following dilation of the pupil, continued slit-lamp biomicroscopic examination of anterior segment structures with clinical grading of lens opacity

-Fundus slit-lamp biomicroscopic examination, including use of accessory diagnostic lenses, to view the vitreous, retina, macula, vasculature, and optic nerve

-if changes on exam or ancillary testing are noted, fundus photography and autofluorescence should be utilized if clinically indicated.

To account for major holidays and unforeseen events such as inclement weather, scheduled visits and testing can occur +/- 1 week, as long as there is documentation as to why they did not occur according to intended schedule. Archival tumor tissue can be obtained at any point during study enrollment and treatment timeline

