9.4.3 Evaluation of Best Overall Response

The best overall response is the best response recorded from the start of the treatment until disease progression/recurrence (taking as reference for progressive disease the smallest measurements recorded since the treatment started). The patient's best response assignment will depend on the achievement of both measurement and confirmation criteria.

Target Lesions	Non-Target Lesions	New Lesions	Overall Response	Best Overall Response when Confirmation is Required*
CR	CR	No	CR	> 4 wks. Confirmation**
CR	Non-CR / Non-PD	No	PR	
CR	Not evaluated	No	PR	>4 wks. Confirmation**
PR	Non-CR / Non-PD / not evaluated	No	PR	
SD	Non-CR / Non- PD/not evaluated	No	SD	documented at least once > 4 wks. from baseline**
PD	Any	Yes or No	PD	
Any	PD***	Yes or No	PD	no prior SD, PR or CR
Any	Any	Yes	PD	

Table 8 Determination of Best Overall Response

* See RECIST 1.1 manuscript for further details on what is evidence of a new lesion.

** Only for non-randomized trials with response as primary endpoint.

*** In exceptional circumstances, unequivocal progression in non-target lesions may be accepted as disease progression.

Note: Patients with a global deterioration of health status requiring discontinuation of treatment without objective evidence of disease progression at that time should be reported as "*symptomatic deterioration*." Every effort should be made to document the objective progression even after discontinuation of treatment.

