11.3 Endpoints

- Objective Response will be scored using RECIST. The objective response rate is defined as the percentage of patients who achieve a complete or partial response. Following an intent-to-treat analysis plan, all patients who receive at least one dose of the combination regimen will be included in the analysis of response.
- Duration of response: from time of first catageroization as a PR or CR to the time of progressive disease.
- Safety: NCI Common toxicity criteria (CTCAE v5.0) will be employed to grade toxicities.

- Progression-free survival will be defined as days from start of treatment to first documented disease progression, death due to any cause or last patient contact. Patients who are alive and have not progressed at the time of statistical analysis will be censored on the most recent date that progression-free status is documented (i.e., imaging date). For patients treated beyond progression (in the setting of an isolated lesion) with consent of study chair, PFS will be time to first progression but time to second progression will be recorded separately.
- Overall survival will be defined as days from start of treatment to death due to any cause or last patient contact. Patients who are alive at the time of statistical analysis will be censored for survival.
- Biomarkers: PPT1, LC3, ALDH1A1 and HLTF will be measured in pre-treatment tissue and at Week 6.
- Median number of autophagic vesicles/cell in tumor tissue
- HCQ PK-PD (See Section 11.5)

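### After the End of Treatment scan, patients who stop without RECIST progression have no fixed imaging interval, and the PFS rules cover neither symptomatic deterioration nor new therapy and give two censoring dates

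*Combined protocol and SAP*

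**What the plan says.** **On treatment.** Footnote 9 of the Study Calendar (section 8.0) reads "Tumor imaging to be performed after every 2 cycles(approximately every 2 months after C1D1 on D21-D28 of applicable cycle". Cycles last 28 days, so the interval is 8 weeks. Footnote 6 fixes the dates: "Tumor imaging timing should follow calendar days and should not be adjusted for delays in cycle starts or extension of cycle duration".

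**At discontinuation.** The calendar marks tumor imaging in the End of Treatment column, and that mark carries no discretion footnote.

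**After discontinuation.** Footnote 5 says "Subjects who discontinue study treatment in the absence of disease progression will have post-treatment follow-up as per standard of care for disease status", and ends this follow-up at progression, new cancer treatment, consent withdrawal, loss to follow-up or death. Footnote 13 adds "Tumor imaging in post-treatment follow-up will be performed per routine care and at the discretion of the treating investigator". The Summary says "All subjects will be evaluated per study calendar for 6 months after discontinuation of study treatment". Section 4.5 says "Subjects will be evaluated for at least 6 months after discontinuation of study treatment" and gives no imaging interval.

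**Symptomatic deterioration.** The note in 9.4.3 makes it a separate reporting category without objective progression, and adds "Every effort should be made to document the objective progression even after discontinuation of treatment".

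**PFS.** Events in 9.4.5 and 11.3 are first progression or death from any cause. Neither section mentions deterioration or new therapy. Section 9.4.5 ends follow-up at the last contact alive and progression-free. The definition sentence in 11.3 also names last contact, but its censoring sentence says that patients alive without progression "will be censored on the most recent date that progression-free status is documented (i.e., imaging date").

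**Duration of response.** In 11.3 it runs from first response to progressive disease, with no rule for death or censoring.

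**The concern.** The protocol foresees several ways to stop without progression: toxicity delays beyond 28 days, compliance below 80% and refusal (9.4.7), and intercurrent illness or investigator decision (calendar footnote 12). For these patients, the date on which progression can be found depends on local practice in an open-label, single-arm trial.

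Three mechanisms follow. Progression found on sparser scans is dated later. A patient who deteriorates and is alive without a further scan is censored just when the risk of failure is high, so the censoring is informative. A patient who deteriorates and dies unscanned contributes an event only at death. If last contact is used as the censoring date, unscanned time is also counted as progression-free. Missed scans cannot be recovered later, and the independent radiology review can read only scans that exist.

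**Working it through.** **1. The plan's own figures.** The documents give no number for PFS or for the share of patients stopping without progression. The only calculated design is the Simon two-stage rule in 11.4 (stop at 1 or fewer responses in 10; success at 6 or more in 29). At a true rate of 10%, the probability of early termination is 0.9^10 + 10 × 0.1 × 0.9^9 = 0.3487 + 0.3874 = 0.7361 (stated 0.74). The exact two-stage binomial gives a false-positive error of 0.0471 (stated at most 0.05) and power of 0.8051 at 30% (stated at least 0.80). The design reproduces. It counts responses and uses no event times, so this point does not touch it.

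**2. Detection lag.** With scans every k weeks, the mean lag from progression to detection is about k/2: 4 weeks on the 8-week grid, 6 weeks at 12 and 8 weeks at 16. The 12- and 16-week intervals are assumptions.

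**3. Six-month PFS.**
- *Assumed inputs:* exponential time to failure with a true median of 3 months; 20% of failures are symptomatic deterioration; survival after failure of 2 to 4 months; 12 months of follow-up.
- *From the documents:* the 8-week on-treatment grid.
- *Method:* 200,000 simulated patients per scenario, Kaplan-Meier estimate S(t) = Π(1 − d/n). Failures other than deterioration are dated at the next 8-week scan, or at death if earlier. Only the dating of deterioration cases changes:

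| How deterioration cases are dated | 6-month PFS |
|---|---|
| Event on the deterioration date | 0.27 |
| 8-week grid continued after stopping | 0.277–0.278 |
| Routine scans every 12–16 weeks | 0.287–0.295 |
| End of Treatment scan detects 80% (assumed) | 0.28–0.29 |
| End of Treatment scan detects 50% (assumed) | 0.30–0.31 |
| Never detected; event at death, or censored at last scan | 0.32–0.34 |

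The effect of the imaging interval alone is 0.287 − 0.277 = 0.010 to 0.295 − 0.278 = 0.017. The ceiling, against counting deterioration as an event, is 0.32 − 0.27 = 0.05 to 0.34 − 0.27 = 0.07. With a true median of 4.5 months, the never-detected case gives 0.46–0.48 against 0.42.

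**4. Median PFS.** With 30% deterioration and a true median of 3 months, the Kaplan-Meier median is 3.68 months with 12- to 16-week scans, the same as when deterioration is counted as an event. It reaches 4.08 to 4.91 months only if nothing is ever detected.

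**5. Direction, by a second model.** Assumed: true median 17 weeks, 20% stopping early, median 26 weeks from progression to death. Restricted mean PFS to 52 weeks is 25.0 weeks if the 8-week grid continues. For stops at random times it is 25.5 weeks with 12-week scans, 25.8 with 16-week scans and 26.6 with 24-week scans. For deterioration-like stops censored at a clear End of Treatment scan it is 27.5. It is 24.4 if symptoms trigger a scan within 2 weeks of progression. Over true medians of 13 to 26 weeks and 10% to 30% stopping early, the shift runs from about −0.8 to +5.3 weeks.

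**6. Duration of response.** At a 30% response rate, 0.30 × 29 = 8.7, or about 9 responders. If 10% to 30% of them stop without progression, 1 to 3 patients are affected.

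**The case against.** A reader might infer that these patients are scanned only at the investigator's discretion. The calendar does not support that: it marks an End of Treatment scan for everyone. If that scan shows progression, the event is dated on time. This stands, but a clear End of Treatment scan leaves all later detection unscheduled.

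A reader might also infer that the Summary is contradicted. It is not. The Summary refers to the study calendar, and footnotes 5 and 13 are part of that calendar. At most, its wording suggests fixed assessments that the calendar does not supply.

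A third tempting reading is that PFS *is* overstated. The direction is not certain, since prompt symptom-triggered scans can date progression earlier than the grid. Under the imaging-date rule in 11.3, a living patient's own time is not lengthened; the bias enters through the Kaplan-Meier estimate if those censored are sicker. The request in 9.4.3 to document progression after stopping also makes zero detection a worst case, though it sets no interval.

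Finally, PFS is secondary, descriptive and without a comparator. At N = 29 the standard error of a proportion of 0.27 is √(0.27 × 0.73 / 29) = 0.08, larger than every shift above. That limits the consequence. It does not justify leaving the event and censoring rules open.

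**Conclusion.** The point holds as a risk of bias, mainly upward, in secondary PFS and duration of response. After the End of Treatment scan there is no fixed imaging interval for patients without progression, disease follow-up ends at new therapy, deterioration and new therapy are in neither PFS definition, and 9.4.5 and 11.3 give different censoring dates. The likely effect is small: about 0.01 to 0.02 in 6-month PFS with 12- to 16-week routine scans, and no movement in the median. The ceiling of 0.32 to 0.34 against 0.27 requires that progression is never detected after stopping. All these sizes rest on the assumed 20% deterioration, 3-month median and post-failure survival, none of which the documents give. The documents support neither a contradiction with the Summary nor a threat to the response-rate decision.

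**What to change.** 1. In 11.5, add a PFS sensitivity analysis that counts symptomatic deterioration and the start of new anti-cancer therapy as events on those dates. The main PFS definition can stay.
2. Reconcile 9.4.5 and 11.3 so that patients alive without progression are censored on the last imaging date showing no progression.
3. Where feasible, reword footnote 13 so that patients off treatment without progression keep the trial's own on-treatment imaging interval until progression, new therapy, withdrawal or death. Of the three changes, only this one also protects duration of response.

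The first two cost one extra Kaplan-Meier run and a wording change. The third costs a few retimed or added scans in a minority of patients.

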9.0 MEASUREMENT OF EFFECT

For the purposes of this study, patients should be re-evaluated for response every 2 cycles. In addition to a baseline scan, confirmatory scans should also be obtained (not less than 4) weeks following initial documentation of objective response.

Response and progression will be evaluated in this study using the new international criteria proposed by the revised Response Evaluation Criteria in Solid Tumors (RECIST) guideline (version 1.1) [*Eur J Ca* 45:228-247, 2009]. **Investigator assessment of RECIST response will be used to make treatment decisions in real time.** Scans will also be submitted for independent radiology review by the RECIST core in batches quarterly to provide an independent measure of response for research purposes. The investigator assessments and the independent radiology assessments will be reported separately. Changes in the largest diameter (unidimensional measurement) of the tumor lesions and the shortest diameter in the case of malignant lymph nodes are used in the RECIST criteria.

9.1 Definitions

Evaluable for toxicity. All patients will be evaluable for toxicity from the time of their first treatment with combined treatment with B and HCQ.

Evaluable for objective response. Only those patients who have measurable disease present at baseline, have received at least one cycle of therapy, and have had their disease re-evaluated will be considered evaluable for response. These patients will have their response classified according to the definitions stated below. (Note: Patients who exhibit objective disease progression prior to the end of cycle 1 will also be considered evaluable.)

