11.4 Simon 2-stage Design

After treatment with standard of care chemotherapy or chemo-immunotherapy, the standard of care for the treatment of progressive NSCLC is docetaxel. The ORR to docetaxel is 14% (Garon et al Lancet 2014). This experimental regimen will be considered not worthy of further development if the ORR is 10% (clearly inferior to docetaxel) and considered worthy of further development if the ORR is 30%.

- Stage 1: Ten patients will be entered into the first stage of the study. If 1 or fewer of these 10 patients respond, then the trial will be terminated. If at least 2 of these 10 patients respond, then proceed to Stage 2.
- Stage 2: Nineteen additional will be entered (total of 29) into the second stage of the study. If 5 or fewer of the 29 patients respond, then it will be concluded that the regimen does not merit further investigation. If 6 or more of the 29 patients respond, then it will be concluded that the regimen does merit further investigation.

The trial is designed with the following characteristics:

- False positive error: If the true response rate is 10%, then the probability of recommending the regimen for further investigation, is no more than 0.05.
- Power: If the true response rate is 30%, then the probability of recommending the regimen for further investigation, is at least 0.80.
- If the true response rate is 10%, then the probability of early termination (PET) is 0.74 after 10 patients have been treated.

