11.5 Plans for Data Analysis

Primary

- The objective response rate and 95% exact confidence interval will be calculated.
- All observed toxicities will be graded and tabled (worse grade experienced in all cycles). The
 overall rate of > grade 3 toxicity and 95% exact confidence interval will be calculated.

Secondary

• Progression-free survival and overall survival will be estimated by the method of Kaplan and Meier. Median values and 95% confidence intervals will be calculated.

Exploratory

- Associations between objective response and expression of biomarkers pre-treatment will be tested using nonparametric Wilcoxon rank sum test. Comparisons of pre- and post-treatment biomarker expression will be conducted using Wilcoxon signed ranks test for paired data.
- Describe autophagic vesicles/cell in tumor tissue at various time points using descriptive statistics and scatter plots.
- To evaluate HCQ pharmacokinetics and pharmacodynamics to determine whether changes in blood-based autophagy biomarkers (ctDNA KRAS allelic frequency) reflect tissue-based changes in autophagy (autophagic vesicles/cell), the nonlinear mixed–effects modeling approach (NONMEM) will be used to perform a full population PK analysis. PK-PD analyses to be conducted by University of Sciences of Philadelphia. Analysis methods – See Section 18. The key variables for the population include the Cmax and half life. Population PK will be assessed and qualitatively compared to population PK findings from other HCQ studies. No hypothesis testing will be performed for any of the vairables.

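### Section 9.1 restricts who is evaluable for response, section 11.3 analyses everyone dosed, and nothing reconciles them; 11.3 is the better reading for the primary ORR, but applying 9.1 would usually raise it

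*Combined protocol and SAP*

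**What the plan says.** Two places define who counts for response.

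- **Section 9.1 (Definitions)** opens with an exclusive condition. Only patients with measurable disease at baseline who "have received at least one cycle of therapy, and have had their disease re-evaluated will be considered evaluable for response" qualify, and it is these patients whose response is classified. A note adds patients with objective progression before the end of cycle 1.
- **Section 11.3 (Endpoints)** defines the ORR and then states, under an intent-to-treat label, that "all patients who receive at least one dose of the combination regimen will be included in the analysis of response".

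Section 11.5 gives the primary analysis as "The objective response rate and 95% exact confidence interval will be calculated" and names no patient set. Section 11.4 states the Simon rule in patients entered ("Ten patients will be entered into the first stage of the study") and describes early stopping in patients treated ("the probability of early termination (PET) is 0.74 after 10 patients have been treated"). The Study Summary caps enrolment at "Total: Up to 29 patients", and section 11.6 gives a range of 10 to 29. No replacement rule appears anywhere.

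Two further passages show who could fall between the two sets. Section 9.4.3 foresees "Patients with a global deterioration of health status requiring discontinuation of treatment without objective evidence of disease progression at that time". Footnote 9 of the Study Calendar (section 8.0) sets the first on-treatment scan: "Tumor imaging to be performed after every 2 cycles(approximately every 2 months after C1D1 on D21-D28 of applicable cycle".

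**The concern.** The two rules give different denominators for the primary efficacy endpoint. Measurable disease is an entry criterion (section 3.1), so that part of 9.1 removes no eligible patient. The other two conditions can. Two groups are in the 11.3 set but outside the 9.1 set:

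1. patients who die, deteriorate or stop during cycle 1 without objective progression;
2. patients who complete cycle 1 but die or stop before any re-evaluation.

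Few in either group could be recorded as responders, so removing them shrinks the denominator and leaves the numerator almost untouched. At stake are the reported ORR and its interval in a single-arm, open-label trial, where the estimate is read directly against the 10% and 30% benchmarks of section 11.4. The choice of denominator should not be open once the results are known.

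A smaller gap remains even under 11.3. No text says outright how to score a dosed patient with no post-baseline assessment, and Table 8 has no row for one.

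**Working it through.** **1. The plan's own design figures.** Inputs from section 11.4: 10 patients in stage 1, stop at 1 or fewer responses; 19 more in stage 2, positive at 6 or more of 29; null rate 10%, target rate 30%.

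- Early termination at 10%: P(X1 ≤ 1 | n = 10) = 0.3487 + 0.3874 = 0.736 (stated 0.74).
- Probability of a positive result: sum over x1 = 2 to 10 of P(X1 = x1) × P(X2 ≥ 6 − x1 | n = 19). At 10% this is 0.047 (stated: no more than 0.05). At 30% it is 0.805 (stated: at least 0.80).

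The stated figures reproduce when 10 and 29 are the patients counted.

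**2. When the first re-evaluation falls.** Cycles last 28 days and the first scheduled scan is on days 21 to 28 of cycle 2, which is study day 28 + 21 = 49 to 28 + 28 = 56. A patient who leaves before then is re-evaluated only if the end-of-treatment scan in the Study Calendar is obtained or an unscheduled scan is done.

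**3. Effect on the ORR.** If k of 29 dosed patients fall outside 9.1 and none responded, the ORR goes from x/29 to x/(29 − k), a multiplication by 29/(29 − k). The documents give no value for k; 2, 4 and 6 are assumptions. Intervals are exact (Clopper-Pearson) 95%.

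| k excluded | Factor | 6 responders (success boundary) | 9 responders (near the 30% target) |
|---|---|---|---|
| 0 | 1.00 | 6/29 = 20.7% (8.0 to 39.7) | 9/29 = 31.0% (15.3 to 50.8) |
| 2 | 1.07 | 6/27 = 22.2% (8.6 to 42.3) | 9/27 = 33.3% (16.5 to 54.0) |
| 4 | 1.16 | 6/25 = 24.0% (9.4 to 45.1) | 9/25 = 36.0% (18.0 to 57.5) |
| 6 | 1.26 | 6/23 = 26.1% (10.2 to 48.4) | 9/23 = 39.1% (19.7 to 61.5) |

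The shift runs from 1.5 points (22.2 − 20.7) to 8.1 points (39.1 − 31.0), and is zero if nobody falls in the gap. With 6 responders, the lower limit passes the 10% null rate only at k = 6.

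**4. Direction is not guaranteed.** A patient who stopped within cycle 1 but later showed a response would also be outside 9.1. If 1 of 4 excluded patients had responded, 6/29 = 20.7% would become 5/25 = 20.0% (6.8 to 40.7%).

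**5. Effect on the decision.** The Simon rule is a count. Dropping non-responders without replacing them leaves the count, and so the decision, unchanged. Replacement would be different. Suppose a fraction m of dosed patients is non-evaluable, none of them responds, and enrolment continues until 10 and then 29 are evaluable. A true all-treated rate of 10% is then 0.10/(1 − m) among those counted:

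| m (assumed) | Rate among evaluable | False positive probability |
|---|---|---|
| 5% | 10.5% | 0.058 |
| 10% | 11.1% | 0.071 |
| 15% | 11.8% | 0.088 |
| 20% | 12.5% | 0.110 |

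All four exceed the stated 0.05.

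**The case against.** The strongest reply is that section 11.3 already settles the matter. Its all-dosed sentence directly follows the definition of the ORR and sits in the statistical section, and 11.4 counts responses among patients entered. Section 9.1 mentions neither the ORR nor an interval, and its evaluable set is never used in 11.3 to 11.5. On that reading a dosed patient without an assessment has not achieved a response and is a non-responder already.

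Most of this stands. A reader might infer that no text says which set governs the primary ORR; the documents do not support that, because 11.3 assigns a set and 11.4 is consistent with it. A reader might also infer that the trial's error rates are compromised. That is not supported either: replacement is nowhere provided for, and the stated totals of 10 and 29 point away from it.

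It is also fair that the gap is narrowed. Early objective progressors stay evaluable under 9.1, a scan is scheduled at end of treatment, and section 9.4.3 asks for every effort to document progression after stopping. The numbers excluded above are assumptions, and each shift is small beside the width of the interval at 6/29.

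What the reply does not remove is the exclusive wording of 9.1. It says whose response is classified, it conflicts with 11.3 on its face, and no sentence subordinates it. Non-responder status for unassessed patients is a sensible inference from 11.3, but it is not written down.

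**Conclusion.** The concern holds as an unreconciled conflict between two stated rules, not as a missing denominator. Section 11.3 is the better reading for the primary ORR. If 9.1 were applied instead, the ORR and both limits of its exact interval would usually move upward: by 3.3 points at the success boundary (20.7% to 24.0%) with 4 excluded non-responders, and by 1.5 to 8.1 points over the range examined. This is conditional on 9.1 being used, on an assumed 2 to 6 unassessed patients out of 29, and on those patients being non-responders.

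The go/no-go rule and its error rates (0.047 and 0.805) are unaffected while 10 and 29 are dosed patients and nobody is replaced. The point should be fixed, because the repair is nearly free and closes a route to an upward-biased primary estimate.

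**What to change.** - **Section 9.1:** state that the evaluable set serves a supportive analysis only and that section 11.3 governs the primary analysis.
- **Sections 11.4 and 11.5:** state that the Simon rule, the ORR and its exact interval use all patients with at least one dose of the combination, without replacement, and that dosed patients lacking a post-baseline assessment count as non-responders.

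The cost is protocol wording. Sample size, decision limits and study procedures stay as they are. The one downside is that the reported ORR may be slightly lower than it would be on the evaluable set.
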